10.1.3 Recruitment goals

Based on Yki-Jarvinen et al., I anticipate a 15% drop out rate.(28) Thus, 23 study participants in each substudy will be enrolled to achieve the recruitment goal of 20 longitudinal study participants.

10.1.4 Interim assessment

I will make one interim assessment after reaching one-half of the target accrual for the longitudinal, cross-sectional, and control studies. Using Protocol Version #:6

Obrien-Fleming bounds for each aim's primary analysis with a two-sided test with α -level of 5%, a critical z-value of 2.80 (corresponding to a p-value of 0.0051) will be used to end the study at interim analysis. We will analyze our study's variance and adjust the sample size if needed.

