10.2 STUDY B-C (Aim 3)

10.2.1 Sample size justification

My accrual goal for STUDY B-C is to have a sufficient sample size to conduct multivariable linear regression with 4 degrees of freedom to quantify the effect of the independent variable, mean $TDD_{insulin}$, on the dependent variable, GIR during the last 30 minutes of the clamp study. At a minimum, 10 participants are needed per degree of freedom to conduct this analysis, thus, we will study 30 participants with T1DM and 10 control participants who are otherwise healthy.

Based on Del Prato et al.,(27) I anticipate participants completing the SCD arm will not see a change in GIR during the last 30 minutes of the clamp study compared to baseline, but will see an increase in GIR of at least 0.6 mg/kg/min after completing the LCD arm. This study also suggests the pooled standard deviation of GIR will be 0.8 mg/kg/min. If the true difference in the Δ GIR between LCD and SCD arms for the 30 T1DM participants is 0.6 mg/kg/min, we will be able to reject the null hypothesis that the difference is zero with probability (power) 0.976. The type 1 error probability associated with this test of this null hypothesis is 0.05.

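### The interim stopping rule pairs a critical value of 2.80 with p = 0.0051, which do not match for the t statistics available at half accrual, and no final significance level is stated.

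*Combined protocol and SAP*

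**What the plan says.** Section 10.1.4 (STUDY 1-7) sets the timing: "I will make one interim assessment after reaching one-half of the target accrual for the longitudinal, cross-sectional, and control studies". It then names "Obrien-Fleming bounds for each aim's primary analysis with a two-sided test with" an alpha of 5%, and says that "a critical z-value of 2.80 (corresponding to a p-value of 0.0051) will be used to end the study at interim analysis". Section 10.2.4 repeats the same rule for STUDY B-C at half of T1DM and control accrual.

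The sample sizes are small. Section 10.1.3 says "23 study participants in each substudy will be enrolled to achieve the recruitment goal of 20 longitudinal study participants". Section 10.2.1 says "we will study 30 participants with T1DM and 10 control participants who are otherwise healthy". The analyses in 10.1.2 and 10.2.2 are linear regressions, and 10.1.2 counts 40 participants across the two substudies.

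No section gives a critical level for the final analysis. Section 10.1.1 plans power at a two-sided 5% level, and 10.2.1 says of its power test: "The type 1 error probability associated with this test of this null hypothesis is 0.05".

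**The concern.** A regression coefficient or paired difference tested with an estimated variance follows a t distribution. With about 10 to 20 participants, its tails are clearly heavier than the normal. A sentence that gives both 2.80 and 0.0051 as the threshold then contains two rules. An interim t statistic between 2.80 and roughly 3.2 to 3.7 ends the study under one and lets it continue under the other.

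This is the only stopping threshold based on the outcome data in either part of the study. Read literally as a critical value, it stops falsely more often than the printed 0.0051. The unstated final level leaves a second gap: if the final test is run at the planning alpha of 0.05, nothing offsets the alpha spent at the interim.

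**Working it through.** **Inputs.** Interim threshold 2.80 and p = 0.0051, two-sided 5%, one interim at half accrual (10.1.4, 10.2.4). Target sizes are 20 per STUDY 1-7 substudy (10.1.3), 30 T1DM participants in STUDY B-C (10.2.1), and 40 if groups are pooled (10.1.2; also 30 + 10 in 10.2.1). The interim sizes are therefore 10, 15 and 20. The final level is not given, so 0.05 and 0.048 are both tried.

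**1. The plan's own pair.** 2 × (1 − Φ(2.80)) = 0.0051. Solving the classical two-look O'Brien-Fleming design at overall 5% (correlation √0.5 between looks) gives an interim bound of 2.797 (p = 0.0052) and a final bound of 1.977 (p = 0.0480). The printed pair is right on the z scale. On that scale, 2.80 then 1.977 gives an overall error of 5.0%, and 2.80 then 1.96 gives 5.2%.

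**2. Is the planning t-based?** Section 10.2.1 takes a difference between "LCD and SCD arms for the 30 T1DM participants is 0.6 mg/kg/min" and states that "the pooled standard deviation of GIR will be 0.8 mg/kg/min". Taking 0.8 as the SD of paired differences, (0.6/0.8) × √30 = 4.11. At alpha 0.05, a central-t approximation on 29 df gives power 0.976, the stated figure; a noncentral t gives 0.978 and a z-test 0.984. At alpha 0.048 the central-t value is 0.975. The stated power fits a t-test at 0.05.

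**3. The two halves on the t scale.** For a paired test, df = n − 1.

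| Interim n | df | two-sided p at t = 2.80 | t needed for p = 0.0051 | p at 2.80 ÷ 0.0051 |
|---|---|---|---|---|
| 10 | 9 | 0.0207 | 3.68 | 4.1 |
| 15 | 14 | 0.0142 | 3.32 | 2.8 |
| 20 | 19 | 0.0114 | 3.16 | 2.2 |

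In a regression with four predictors and one observation per participant, df = n − 5. The p-value at 2.80 is then 0.038 (5 df), 0.019 (10 df) or 0.0135 (15 df).

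**4. Overall two-sided type 1 error.** Paired t-tests were simulated under the null, 2,000,000 runs per row.

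| Interim / final n | t > 2.80, final 0.05 | t > 2.80, final 0.048 | p < 0.0051, final 0.05 | p < 0.0051, final 0.048 |
|---|---|---|---|---|
| 10 / 20 | 6.3% | 6.1% | 5.3% | 5.1% |
| 15 / 30 | 5.8% | 5.6% | 5.2% | 5.0% |
| 20 / 40 | 5.6% | 5.4% | 5.2% | 5.1% |

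So the choice of final level moves the error by about 0.2 point. With the final level at 0.05, applying 2.80 to t rather than using the p-value moves it by 6.3 − 5.3 = 1.0 point at 10/20, 5.8 − 5.2 = 0.6 at 15/30 and 5.6 − 5.2 = 0.4 at 20/40.

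For the four-predictor regression (100,000 runs), t > 2.80 with a final level of 0.05 gives 8.0%, 6.1% and 5.8%. Using p < 0.0051 with 0.048 gives 5.3%, 5.0% and 5.1%.

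**The case against.** The quoted sentence is correct as written for a z-value, and 2.80 is the right classical bound. The plan never says that a raw t statistic will be compared with 2.80. Applying a group-sequential bound through its nominal p-value is standard practice, and that p-value is printed beside it. On that reading the overall error is 5.0% to 5.3% whichever final level is used. Naming O'Brien-Fleming bounds at an overall 5% also implies a final level of 0.048, so the 0.05 in 10.1.1 and 10.2.1 can be read as a planning alpha only. Finally, the degrees of freedom are not fixed by the documents: pooling shrinks the gap, while covariate adjustment without pooling widens it.

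All of this stands, and it limits the point. A reader might infer that the 2.80 and 0.0051 pair is itself miscalculated, that the plan tests the final analysis at 0.05, or that the trial's type 1 error is about 6%. The documents support none of these. The pair is right for z, the final rule is unwritten, and about 6% needs 2.80 to be applied to the t statistic.

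What the objection does not remove is the ambiguity. The sentence makes the critical value the operative threshold and adds the p-value in parentheses. Nothing says that the p-value governs, and the implied final level appears nowhere.

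**Conclusion.** The stopping rule is wrong as written for the tests that will be run. Its two halves agree only for a normal statistic, and they diverge at every plausible interim size. The consequence depends on which half is followed: an overall error of 5.4% to 6.3% if 2.80 is applied to t, or 5.0% to 5.3% if p < 0.0051 governs.

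These ranges assume paired t-tests with the interim at exactly half of 20, 30 or 40 participants, and a final level of 0.05 or 0.048. The size is modest, and most of it comes from the scale of the interim statistic rather than from the final level. It is still worth correcting because it concerns a decision to stop, and it must be settled before interim data are seen.

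**What to change.** In 10.1.4 and 10.2.4, replace the z-value with this rule: stop only if the two-sided p-value from the t or regression test of that aim's primary analysis is below 0.0051. In the same sections, state that the final analysis is significant only at p < 0.048. Align the alpha wording in 10.1.1 and 10.2.1: overall 5%, final nominal level 0.048. Both interim sections also allow the sample size to be adjusted after the look. The 0.048 assumes that the interim falls at half of the final sample, so add that the final level will be recalculated if the size changes.

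The cost is a few sentences and a slightly stricter final test. Aim 3 power falls by about 0.1 percentage point (0.976 to 0.975 by the plan's apparent method). For the T1DM GIR comparison in Table 7, the SD of differences is 2.7 × √(2 × (1 − 0.79)) = 1.75. With n = 20 and a difference of 1.3, power goes from 0.883 to 0.879.

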10.2 STUDY B-C (Aim 3)

10.2.1 Sample size justification

My accrual goal for STUDY B-C is to have a sufficient sample size to conduct multivariable linear regression with 4 degrees of freedom to quantify the effect of the independent variable, mean $TDD_{insulin}$, on the dependent variable, GIR during the last 30 minutes of the clamp study. At a minimum, 10 participants are needed per degree of freedom to conduct this analysis, thus, we will study 30 participants with T1DM and 10 control participants who are otherwise healthy.

Based on Del Prato et al.,(27) I anticipate participants completing the SCD arm will not see a change in GIR during the last 30 minutes of the clamp study compared to baseline, but will see an increase in GIR of at least 0.6 mg/kg/min after completing the LCD arm. This study also suggests the pooled standard deviation of GIR will be 0.8 mg/kg/min. If the true difference in the Δ GIR between LCD and SCD arms for the 30 T1DM participants is 0.6 mg/kg/min, we will be able to reject the null hypothesis that the difference is zero with probability (power) 0.976. The type 1 error probability associated with this test of this null hypothesis is 0.05.

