Iatrogenic hyperinsulinemia's contribution to IR early in the course of T1DM is unestablished. IR is independently correlated with macrovascular disease in T1DM. (20-22) My previous human subjects research strongly implicated iatrogenic hyperinsulinemia as the primary driver of IR in T1DM (see preliminary data). This work aligned with that of others who induced chronic hyperinsulinemia using differing approaches: overexpressing insulin gene expression in the mouse(23, 24), delivering excess insulin into the hepatic portal vein of dogs(25), and infusing insulin into a peripheral vein of healthy humans for 2-3 days(26, 27). A common theme throughout these studies is that chronic hyperinsulinemia evokes a downregulation of insulin sensitivity. Although Yki-Järvinen et al. found insulin sensitivity improved during the partial clinical remission (PCR, a.k.a. "Honeymoon") phase, the contribution of decreased iatrogenic hyperinsulinemia to the enhanced insulin sensitivity adjusted for other covariates has not been examined.(28) We will determine this relationship in Aim 1.

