6.2 Research visits: STUDY B-C (Aim 3)

Each subject will participate in three research visits to complete participation as depicted in figure 7. The first visit (“SCREEN” in figure 7C) will determine the potential participant’s eligibility and allow the study team to provide instructions to the participants. If the participant meets eligibility criteria he/she will begin a 1-2-week “run-in” period within six weeks of the screening visit. After the run-in period, the participant will be randomized to consume either 1 week (+/- 1 day) of a standard carbohydrate diet (SCD) or 1 week (+/- 1 day) of consuming a low carbohydrate diet (LCD) as shown in figure 7. On the final day of the intervention, the participant will consume a standardized 2,000 kilocalorie SCD or LCD provided by the study team. After a week (+/- 1 day) of being on either intervention, participants will report to the CRC for the first of two “STUDY” visits, where insulin sensitivity and endothelial dysfunction will be assessed (STUDY B). Following STUDY B, participants will begin a washout period of approximately 3 weeks where they will resume their usual diabetes management. The study team will schedule STUDY C to follow STUDY B by no more than one month in male participants. For female participants, STUDY B and C will occur during the follicular stage of consecutive menstrual cycles (i.e., day 2-10 of the menstrual cycle). For 1 week (+/- 1 day) preceding STUDY C, each participant’s intervention will cross-over to either LCD or SCD. On the final day of the second intervention, the participant will again consume a standardized 2,000 kilocalorie SCD or LCD provided by the study team. Upon completion of the second 1-week (+/- 1 day)

treatment period, each participant will return to the CRC for a second and final assessment of insulin sensitivity and endothelial dysfunction (STUDY C).

Each research visit and intervention period is discussed in the following subsections.

[figure not shown]

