10.0 Statistical Considerations

10.1 STUDY 1-7 (Aims 1-2)

10.1.1 Sample Size Justification

My accrual goal is to obtain an adequate number of participants within both the T1DM SUBSTUDY (STUDY 1-3) and CONTROL SUBSTUDY (STUDY 4-7) to ensure greater than 80% statistical power ($1-\beta$) for a two-sided α -level of 5% for each specific aim's primary outcome. The sample size calculations used the best-available previously published descriptions of insulin sensitivity(28, 105) and %FMD(7, 30, 106-108) in T1DM. Table 7 summarizes these calculations.

Table 7: Key parameters for sample size calculations for T1DM and CONTROL substudies. n , δ , $1-\beta$, σ , and r represent the sample size, the expected minimum difference, statistical power, overall standard deviation, and longitudinal correlation, respectively, for each key outcome. * indicates calculations based on preliminary data as previously described. [†] The detectable differences for GIR of 1.3 to 2.2 mg/kg/min represent a 20% to 21% change in outcomes. [‡] The detectable differences for %FMD of 2.2% to 4.3% represent a 25% to 39% change in outcomes.

Aim	T1DM Substudy					Control Substudy						
	Key Outcome for Power Calculation	n	δ	$1-\beta$	σ	r	Key Outcome for Power Calculation	n	δ	$1-\beta$	σ	r
1	GIR between STUDY T ^{LO} vs. T ^{HI} in mg/kg/min	20	1.3	0.88	2.7	0.79	GIR between STUDY C ^{BOTH} vs. C ⁰ in mg/kg/min	20	2.2	0.92	3.5	0.79
2	%FMD between STUDY T ^{LO} vs. T ^{HI}	20	2.2%	0.88	4.3%	0.83	%FMD between STUDY C ^{BOTH} vs. C ⁰	20	4.3%	0.83	3.7%	0.83

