10.2.2 Analysis Plan

The correlation between the independent variable $TDD_{insulin}$ (averaged over 7 days prior to each STUDY B-C visit) and the GIR over the last 30 minutes of the clamp will be determined. Several other explanatory variables could confound this bivariate analysis, however. For example, confounding variables might include treatment order, hyperglycemia, hyperlipidemia, or measures of glycemic variability. For this reason, as with STUDY 1-5, I will use multivariable linear regression analysis to account for the effect of these potential confounders.

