10.2.4 Interim assessment

I will make one interim assessment after reaching one-half of the target accrual for the T1DM and control participants. Using Obrien-Fleming bounds for each aim's primary analysis with a two-sided test with α -level of

5%, a critical z-value of 2.80 (corresponding to a p-value of 0.0051) will be used to end the study at interim analysis. We will analyze our study's variance and adjust the sample size if needed.

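### Aim 3's power of 0.976 needs a within-person GIR difference SD of 0.8; Table 7's T1DM inputs imply 1.75 (power about 0.44), and the protocol does not reconcile the two

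*Combined protocol and SAP*

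**What the plan says.** Section 10.2.1 (STUDY B-C, Aim 3) expects no change in clamp GIR on the standard-carbohydrate diet and a rise of at least 0.6 mg/kg/min on the low-carbohydrate diet. Both the effect and the SD come from a cited study: "This study also suggests the pooled standard deviation of GIR will be 0.8 mg/kg/min". For 30 T1DM participants and a true difference of 0.6, "we will be able to reject the null hypothesis that the difference is zero with probability (power) 0.976". On alpha: "The type 1 error probability associated with this test of this null hypothesis is 0.05". The section gives no within-person correlation. Section 1.0 describes the cited study, together with one other, as "infusing insulin into a peripheral vein of healthy humans for 2-3 days".

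Section 10.1.1, Table 7, plans for the same outcome in T1DM (GIR, mg/kg/min) with n = 20, difference 1.3, SD 2.7, correlation 0.79 and power 0.88. Its caption defines the last two inputs as "overall standard deviation, and longitudinal correlation, respectively, for each key outcome".

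Section 10.2.4 adds, for the interim assessment at half accrual: "We will analyze our study's variance and adjust the sample size if needed".

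**The concern.** The power of a crossover depends on the SD of the within-person difference. A pooled SD of GIR would ordinarily be read as a single-visit SD, which needs a correlation before it can be used in a paired calculation. Section 10.2.1 does not give one, so the reader cannot tell what 0.8 measures.

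The value also sits far from the one the protocol uses elsewhere for the same measurement in the same disease, and no section compares the two. The cited source is described as work in healthy people, while the calculation concerns people with T1DM.

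A stated power of 0.976 invites a reader to treat a null diet comparison as close to conclusive. If Table 7's variability applies, a true effect of 0.6 mg/kg/min would be missed more often than found.

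**Working it through.** **Method.** Paired t-test, two-sided alpha 0.05, noncentral t with n − 1 degrees of freedom and noncentrality δ√n / SD_diff. Where a single-visit SD σ and correlation r are given, SD_diff = σ√(2(1 − r)). Section 10.2.1 does not state sidedness; two-sided is taken from section 10.2.4.

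**1. Reproduce 0.976.** Inputs from 10.2.1: n = 30, δ = 0.6, SD_diff taken as 0.8. Noncentrality = 0.6 × √30 / 0.8 = 4.11. Power is 0.978 by exact noncentral t, or 0.9759 by the shifted-t approximation, which matches the stated 0.976.

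**2. Try other readings of 0.8.**

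| Reading of 0.8 | SD_diff | Power |
|---|---|---|
| Single-visit SD, r = 0 | 1.131 | 0.802 |
| Single-visit SD, r = 0.5 | 0.800 | 0.978 |
| Single-visit SD, r = 0.79 (Table 7) | 0.518 | >0.999 |
| Two independent groups of 30 | n/a | 0.815 |

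Of these, only r = 0.5 returns the stated figure, and it is algebraically the same as SD_diff = 0.8. Section 10.2.1 therefore differs from Table 7 on either reading: in the correlation if 0.8 is a single-visit SD, and in the SD of differences if it is not.

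**3. Check how Table 7 combines its inputs.** T1DM GIR row: SD_diff = 2.7 × √(2 × 0.21) = 1.750. With n = 20 and δ = 1.3, noncentrality = 1.3 × √20 / 1.750 = 3.32 and power is 0.883, against the stated 0.88. So 1.75 is the SD of differences behind that row.

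**4. Put Table 7's T1DM inputs into Aim 3.** With n = 30, δ = 0.6 and SD_diff = 1.750, noncentrality = 1.88 and power is **0.443**. The difference detectable at 80% power is 0.926 mg/kg/min.

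**5. Vary the correlation, holding σ at 2.7** (n = 30, δ = 0.6).

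| r | SD_diff | Power |
|---|---|---|
| 0.50 | 2.70 | 0.22 |
| 0.70 | 2.09 | 0.33 |
| 0.79 | 1.75 | 0.44 |
| 0.82 | 1.62 | 0.50 |
| 0.85 | 1.48 | 0.57 |
| 0.90 | 1.21 | 0.75 |
| 0.95 | 0.85 | 0.96 |

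Power of 80% needs SD_diff no larger than 1.134, so r = 1 − 1.134² / (2 × 2.7²) = 0.912. An SD_diff of 0.8 needs r = 1 − 0.64 / (2 × 7.29) = 0.956.

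**The case against.** The best case for the protocol has five parts.

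- **The arithmetic is right for its input.** This stands. The dispute is over the SD, not the calculation, and the value used can be recovered by working backwards.
- **Aim 3 may well be less variable within a person.** Table 7's T1DM visits span disease phases over about 12 months in recently diagnosed people, with a 120-minute clamp. Aim 3's visits are about a month apart with a 150-minute clamp. Food is supplied the day before, insulin lispro is used for the preceding 24–48 hours, and women are studied in the follicular phase. Section 4.0 also remarks that the crossover design keeps variance between interventions low. This stands as a reason why 0.44 may be too low. But section 4.0 uses its remark only to relax the age criteria, and no section ties these features to 0.8. The gap is also wide: at σ = 2.7, raising r from 0.79 to 0.85 lifts power only to 0.57. A lower single-visit SD is possible too, but equally unargued.
- **Table 7 is an imperfect benchmark.** This stands in part. By the same formula its other three rows do not reproduce: control GIR gives 0.984 against 0.92, T1DM %FMD 0.961 against 0.88, and control %FMD above 0.999 against 0.83. The comparison here uses only the T1DM GIR row, which does reproduce.
- **The interim variance review is a safeguard.** It is a partial one. Section 10.2.4 gives no target SD or adjustment rule, and it leaves 0.976 in the text.
- **Nothing in the design depends on the figure.** True: accrual comes from the rule of ten participants per degree of freedom. The stated power will still colour how a null result is read.

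**Conclusion.** The concern holds. The stated 0.976 requires an SD of within-person differences of 0.8 mg/kg/min, which section 10.2.1 neither states nor justifies for T1DM. The protocol's own T1DM inputs for the same outcome imply 1.75, more than twice as large, and give power of about 0.44.

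The 0.44 is not a proven true power. It assumes that Table 7's SD of 2.7 and correlation of 0.79 carry over to a different T1DM cohort with shorter visit intervals and tighter standardisation. If the SD of 2.7 carries over, power falls below 80% for any correlation under about 0.91, and the stated figure needs about 0.956.

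Two limits apply. Both 0.976 and 0.44 refer to a paired comparison of the two diets. Neither is the power of the regression on total daily insulin dose planned in section 10.2.2, where "I will use multivariable linear regression analysis to account for the effect of these potential confounders". Also, section 10.2.1 words the effect as a change from baseline, but section 6.2 schedules no baseline clamp: "After a week (+/- 1 day) of being on either intervention, participants will report to the CRC for the first of two" assessments. A shared baseline cancels from the diet contrast, so that point concerns wording only.

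**What to change.** In section 10.2.1:

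1. State whether 0.8 is a single-visit SD, giving r, or an SD of within-person differences.
2. Give one SD and one correlation for Aim 3. Reconcile them with Table 7's T1DM row, or justify the difference, for example by the shorter visit interval and the standardisation.
3. Unless 0.8 is justified as a T1DM within-person difference SD, replace the single figure with power over a range of correlations. Include 0.44 at Table 7's inputs and the difference detectable at 80% power (about 0.93 mg/kg/min at those inputs).
4. Say that the figure is the power of the paired low- versus standard-carbohydrate comparison, not of the regression in section 10.2.2.
5. Word the effect as GIR on the low-carbohydrate diet minus GIR on the standard diet.

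The cost is a less favourable stated power. No participants, visits or procedures are added, because the target of 30 T1DM participants rests on the degrees-of-freedom rule and not on this calculation.
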